## **11.5. Follow-up of AEs and SAEs**

After the initial AE/SAE report, the investigator is required to proactively follow each patient and provide further information on the patient's condition. The investigator will ensure that follow-up includes any supplemental investigations as may be indicated to elucidate the nature and/or causality of the AE or SAE. This may include additional laboratory tests or investigations, histopathological examinations, comparison to historical data on toxicity of chemoradiation in this study population or consultation with other health care professionals.

Non-serious AEs that have not resolved by the end of the 30-Day Follow-up Period will be considered ongoing and marked as such in the CRF. All SAEs will be followed until they are resolved or a new baseline is established, at which point the appropriate CRF page(s) or SAE Report Form(s) will be updated.

Routine collection of AEs will stop at the end of the 30-Day Follow-up Period.

As reasonably requested by the Sponsor, the investigator will perform or arrange for the conduct of supplemental measurements and/or evaluations to elucidate as fully as possible the nature and/or causality of the AE or SAE. If a patient dies during participation in the study or during a recognized follow-up period, Galera Therapeutics, Inc. will be provided with a copy of any post-mortem findings, including histopathology.

## **11.6. Post-Study Reporting Requirements**

Although such information may not be routinely sought or collected by Galera Therapeutics, Inc., SAEs that occur after the patient has completed a clinical study may be reported. Such cases will be evaluated for expedited reporting.

## **11.7. Pregnancy**

The risks of treatment with GC4419 during pregnancy have not been evaluated. Male subjects and female subjects of childbearing potential who engage in heterosexual intercourse should use a highly effective method of contraception starting at least on day prior to the first day of treatment and throughout the study and for 30 days (females) or 90 days (males) following the last dose of GC4419.

All females will be considered as of childbearing potential unless they are postmenopausal (eg, amenorrheic for at least 12 consecutive months, in the appropriate age group, and without other known or suspected cause) or have been sterilized surgically (ie, bilateral tubal ligation, total hysterectomy, or bilateral oophorectomy, all with surgery at least 1 month before dosing). Subjects with a vasectomy or a vasectomized partner with confirmed azoospermia are eligible.

If a subject of childbearing potential is neither surgically sterile nor postmenopausal, a highly effective contraceptive method (ie, a method that can achieve a failure rate of less than 1% per year when used consistently and correctly) must start either before and throughout the entire study period and for 30 days after the last dose of Test Article is administered. Highly effective methods of contraception include any of the following:

- total abstinence from heterosexual intercourse (if it is their preferred and usual lifestyle)
- an intrauterine device or intrauterine hormone-releasing system (IUS)
- a contraceptive implant
- an oral contraceptive (Subject must be on a stable dose of the same oral contraceptive product for at least 28 days before dosing and throughout the study and for 28 days after study drug discontinuation)

Pregnant and/or lactating females are excluded.

Pregnancies or exposure to study drug through breastfeeding must be reported as soon as possible but no later than 24 hours from the date the investigator becomes aware of the event. The contact information for the reporting of pregnancies and exposure to study drug through breastfeeding is provided in the Investigator Study File. The outcome of the pregnancy must be reported as soon as possible but no later than 24 hours from the date the investigator becomes aware of the outcome.

A subject who becomes pregnant must be withdrawn from the study.

#### **11.7.1. Time Period for Collecting Pregnancy Information**

As permitted by IRB/EC/REB policies, any pregnancy that occurs from the first dose of GC4419 up to 30 days after last dose should be reported using the appropriate form within 2 weeks of learning of the patient's pregnancy. The patient will be followed throughout the course of the pregnancy. Generally, follow-up will be no longer than six to eight weeks following the estimated delivery date. Any premature termination of the pregnancy should be reported. If a pregnancy is identified outside the 30 days after last dose, the investigator may report using clinical judgment.

#### **11.7.2. Action to be Taken if Pregnancy Occurs in a Female Partner of a Male Patient**

The investigator will attempt to collect pregnancy information on any female partner of a male study patient who becomes pregnant while participating in this study. The investigator will record pregnancy information on the appropriate form and submit it to Galera Therapeutics, Inc. within 2 weeks of learning of the partner's pregnancy. The partner will also be followed to determine the outcome of the pregnancy. Information on the status of the mother and child will be forwarded to Galera Therapeutics, Inc.. Generally, follow-up will be no longer than six to eight weeks following the estimated delivery date. Any premature termination of the pregnancy will be reported. If a pregnancy is identified outside the 30 days after last dose, the investigator may report using clinical judgment.

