### 7.1. Subject Inclusion Criteria

Subjects are required to meet the following inclusion criteria before entering the trial:

1. Subjects scheduled to be treated with (definitive or adjuvant) radiation therapy in combination with chemotherapy once daily for pathologically-confirmed Stage 3 or post-operative Stage 2B NSCLC or limited stage SCLC
2. Treatment plan for subjects show that 5 cm of the esophagus for at least one surface, is included in the 60 Gy isodose volume. Dose volume histograms show esophagus dose exposure meet V38>30% and/or V60>20% (to ensure that there is a similar, significant risk for esophagitis among the subjects).

Note: In case the final planning shows that the contoured esophagus is close to but the 60 Gy isodose does not cover completely 5 cm, this subject may be allowed on the trial at the discretion of the principal investigator after discussion with and review by the Medical Monitor.

3. Age  $\geq$  18 years or older
4. ECOG performance status  $\leq$  2
5. Adequate hematologic function as indicated by:
  - a Absolute neutrophil counts (ANC)  $\geq$  1,500/mm^3
  - b Hemoglobin (Hgb)  $\geq$  9.0 g/dL
  - c Platelet count  $\geq$  100,000/mm^3
6. Adequate renal and liver function as indicated by:
  - a Estimated baseline creatinine clearance  $>60$  cc/min ( $CrCl = (140 - Age) \times Mass (kg) \times [0.85 \text{ if female}] / 72 \times [Serum Creatinine (mg/dL)]$ )
  - b Total bilirubin  $\leq$  1.5 x upper normal limit (ULN)
  - c Aspartate aminotransferase (AST) and alanine aminotransferase (ALT)  $\leq$  2.5 x ULN
  - d Alkaline phosphatase  $\leq$  2.5 x ULN
7. Males and females must agree to use a highly effective contraception starting at least one day prior to the first day of treatment and continuing for 30 days after the last dose of GC4419 (females) or 90 days (males)
8. Properly obtained written informed consent

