## **8. INVESTIGATIONAL PRODUCT AND TREATMENT OF SUBJECTS**

### **8.1. Concomitant Medications**

All concomitant therapies (eg, prescription and over-the-counter medications) taken by subjects from Baseline of Day 1 GC4419 until 30 days following the last GC4419 dose, RT or chemotherapy dose (ie, whichever occurs last) will be collected in the CRF. Additionally, any concomitant therapies if used to treat any serious or related AE will be recorded in the CRF.

Analgesic/narcotic medications will be captured and recorded along with other concomitant medications in the CRF. Narcotic use will be recorded from the baseline visit until 30 days following the last GC4419 dose, RT or chemotherapy dose (ie, whichever occurs last).

Antiemetic prophylaxis and hematopoietic growth factors use should be administered per ASCO guidelines.

Subjects who withdraw consent for further administration of GC4419 should be encouraged to continue and complete standard RT/chemotherapy treatment and other study procedures.

However, if a subject withdraws consent for the study or is removed from the study completely (ie, the subject is no longer participating in any study procedures or follow-up) no further data should be collected after the date of the subject's study discontinuation.

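### Sections 11.7 to 11.7.2 give conflicting pregnancy-reporting rules, and their 30-day discretion falls inside the 90-day contraception period set for men

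*Combined protocol and SAP*

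**What the plan says.** On contraception, section 11.7 asks for a highly effective method "throughout the study and for 30 days (females) or 90 days (males) following the last dose of GC4419". The synopsis and section 7.1, item 7, set the same two periods.

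On reporting, three provisions apply:

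- Section 11.7 says that pregnancies "must be reported as soon as possible but no later than 24 hours from the date the investigator becomes aware of the event". It sets no end date and does not separate subjects from partners.
- Section 11.7.1, for subjects, says that "any pregnancy that occurs from the first dose of GC4419 up to 30 days after last dose should be reported using the appropriate form", and gives 2 weeks from learning of the pregnancy.
- Section 11.7.2, for partners of male subjects, covers a partner who becomes pregnant during participation in the study. It also gives 2 weeks.

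Both subsections end with the same sentence: "If a pregnancy is identified outside the 30 days after last dose, the investigator may report using clinical judgment".

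On what happens to a pregnant subject, section 11.7 says "A subject who becomes pregnant must be withdrawn from the study". Section 11.7.1 says she is followed through the pregnancy, generally for no longer than six to eight weeks past the estimated delivery date. Section 7.5 lists a confirmed positive pregnancy test among the reasons for which study treatment may be discontinued.

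**The concern.** The protocol treats the 90 days after a man's last dose as a period in which conception should be avoided, yet the subsection on partner pregnancies makes reporting a matter of judgment from Day 31. The closing sentence also uses a different trigger from the rule it follows: the rule counts pregnancies that *occur* by Day 30, and the exception counts those *identified* after Day 30. A pregnancy conceived under exposure but recognised late falls under both.

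What is at stake is safety information on individual pregnancies. Section 11.7 says the risks of treatment during pregnancy have not been evaluated, so each exposed pregnancy is informative, and one that is never reported may not be recoverable later. The deadlines and the withdrawal wording are lesser matters of clarity in the same sections.

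**Working it through.** The plan gives no figure to reproduce. The check sets the provisions side by side and uses a few subtractions. Days are counted from the last dose of GC4419.

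**1. Length of the windows.** Inputs: contraception for 30 days (women) and 90 days (men), from the synopsis, 7.1 and 11.7; discretion after 30 days, from 11.7.1 and 11.7.2.

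- Men: 90 − 30 = 60 days of the contraception period (Days 31 to 90) lie beyond the cut-off.
- Women: 30 − 30 = 0 days, if the cut-off is read by date of occurrence.

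**2. Which rule applies to which case.**

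| Case | Section 11.7 | Subsection's own scope | Closing sentence |
|---|---|---|---|
| Partner pregnancy conceived and identified in Days 31 to 90 | report | within 11.7.2 if the man is still participating (visits run to 1 year post-RT, section 10.8.2) | discretionary |
| Female subject, conceived on the last dosing day, identified on Day 40 | report | within 11.7.1, occurred by Day 30 | discretionary |

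In both cases two provisions call for a report or for collection of information, and the third leaves it to judgment. Nothing in 11.7 says which prevails.

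**3. Effect of the identification trigger.** Let L be the lag from conception to identification. The documents give no value, so L is an assumption. Under the closing sentence, the latest conception still outside the discretion is on Day 30 − L:

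- L = 14 days: 30 − 14 = Day 16
- L = 28 days: 30 − 28 = Day 2
- L = 56 days: 30 − 56 = Day −26, that is, 26 days before the last dose and inside a course of about 6 weeks

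The trigger can therefore reach conceptions during dosing if recognition is slow. Late recognition in women is possible, because the serum pregnancy test is scheduled at screening only (section 10.6 and Appendix 1).

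**4. Other routes of capture.** Routine adverse-event collection stops 30 days after the last dose of RT, chemotherapy or GC4419, whichever is last (11.2.2, 11.5). The 90-day visit records only updates to serious events already ongoing at the 4-week visit (10.8.1). A congenital abnormality is a seriousness criterion (11.1.2), but events after study completion are not necessarily sought (11.6). These routes are a partial backstop and do not replace a pregnancy report.

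**5. Deadlines.** 2 weeks = 14 × 24 = 336 hours, against 24 hours. A report made within 24 hours satisfies all three sections. A report made on day 14 satisfies 11.7.1 or 11.7.2 and breaches 11.7. Either way the report is made.

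**6. Withdrawal and follow-up.** Section 8.1 says that "no further data should be collected after the date of the" subject's discontinuation. It limits this to subjects who withdraw consent for the study or are removed completely, which it explains as taking part in no procedure and no follow-up. A woman followed under 11.7.1 is still in follow-up, so the bar does not reach her. What remains is that 11.7 requires withdrawal without saying that pregnancy follow-up goes on.

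**The case against.** The strongest reply is that section 11.7, the parent section, already requires pregnancies to be reported, with no time limit, and that 11.7.2 covers partner pregnancies throughout participation. On that reading the closing sentence concerns only pregnancies outside those rules. This stands in part. A reader might infer that reporting simply becomes optional after Day 30 and that 60 of the 90 days are lost. The documents do not support that: 11.7 and the opening of 11.7.2 point the other way, so the defect is a conflict between rules. The 60 days measure a mismatch between windows and are not a share of pregnancies lost.

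Two further inferences should be set aside. One is that the differing deadlines cause pregnancies to be missed. They can delay a report but do not remove it, and they can coexist if 24 hours means first notice and 2 weeks means the completed form. The protocol does not say so, and a clarification is enough. The other is that section 8.1 forbids data collection on a subject withdrawn for pregnancy. Its own definition of complete removal rules that out.

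It is also fair to say that a duty to report partner pregnancies whenever they are identified would have no end date, while 11.7.2 promises only an attempt at collection. The fix should therefore be limited to pregnancies that the investigator learns of.

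What survives is that the closing sentence appears in both subsections without reconciliation, is shorter than the male contraception period, and uses a different trigger from the rule it qualifies.

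**Conclusion.** The point holds as a conflict in the reporting rules. After Day 30, section 11.7 and the opening of 11.7.2 call for a partner pregnancy to be reported or followed up, while the closing sentence leaves reporting to judgment, inside a period in which the protocol still requires contraception in men. For women the windows agree at 30 days by date of occurrence, and the conflict arises only from the switch to date of identification. A site that follows the closing sentence could leave an exposed pregnancy unreported.

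The number of such cases cannot be derived from the documents. Few are expected among about 60 lung cancer patients, and the consequence is per case. The lag figures rest on an assumed 14 to 56 days to recognition and show only the direction of the effect. Sample size, power and the primary analysis are unaffected. The deadline and withdrawal wording needs clarification and does not by itself lose data.

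**What to change.** 1. In 11.7.1 and 11.7.2, tie the reporting duty to estimated conception from first dose through the end of the contraception period that the protocol already sets: 30 days after the last dose for female subjects, 90 days for partners of male subjects. Apply it to any such pregnancy the investigator learns of, and delete the identification-based discretion within that period.
2. Reconcile the deadlines across 11.7, 11.7.1 and 11.7.2, for example by stating that 24 hours is for initial notification and 2 weeks for the completed form.
3. Add one sentence to 11.7 saying that withdrawal for pregnancy does not end pregnancy follow-up.
4. The sponsor should reconcile 7.5 and 11.7 on treatment discontinuation and study withdrawal; no view is taken here on which rule is right.

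The cost is wording in a few short sections, with no new visit or procedure, and at most a few more pregnancy reports.

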### **11.8. Regulatory Reporting of Adverse Events**

Galera Therapeutics, Inc. will have final determination of reportability and is responsible for notifying the relevant regulatory authorities of certain events. The investigator will report all SAEs that occur at his/her site to the IRB per the site's IRB regulations. AEs will be reported to regulatory authorities in compliance with 21 Code of Federal Regulations (CFR) 312.32, local and regional law and established guidance by the Sponsor or its designee. The format of the reports will be dictated by the local and regional requirements.

Investigators will also be notified of all unexpected, serious, drug-related events (7/15 Day Safety Reports) that occur during the clinical trial. Each site is responsible for notifying its IRB/IEC/REB of these additional SAEs in accordance with local or central IRB/IEC/REB procedures. Copies of each report will be kept in the investigator's files and adequate documentation will be provided to Galera Therapeutics, Inc. including documentation that the IRB/IEC/REB was notified of each safety report.

## 12. STATISTICS

### 12.1. General Considerations

A separate statistical analysis plan will provide technical details of the statistical analyses to be performed, in addition to the specifications in this protocol.

All statistical analyses will be conducted with the SAS® software package version 9.2 or higher.

### 12.2. Sample Size

Approximately 60 subjects will be enrolled to ensure that 55 subjects are evaluable for the primary analysis, with an assumed proportion of early discontinuations without previous  $\geq$  Grade 2 esophagitis of approximately 10%.

The incidence of  $\geq$  Grade 2 esophagitis will be summarized and compared descriptively with historical controls based incidence rate of 30% for chemoradiotherapy alone ([Palma 2013](#), [Kwint 2012](#), [Fogh 2016](#)).

For illustration, with 55 patients in the primary analysis, the 95% Clopper-Pearson confidence interval around an observed incidence of  $\geq$  Grade 2 esophagitis (NCI-CTCAE) of 16% (9/55) would be 8% to 29%.

Assuming that the true incidence of  $\geq$  Grade 2 esophagitis in GC4419-treated subjects is 13%, the trial will have roughly 80% power with 55 subjects in the analysis to demonstrate incidence lower than 30% with a one-sided Type I error rate of 2.5%.

### 12.3. Analysis Populations

The primary efficacy population will include all subjects who receive at least one dose of GC4419 and either a) complete their RT course or b) discontinue their RT course early but are known to have had acute radiation esophagitis. Sensitivity analyses will also be performed to assess the effect on estimated incidence when including GC4419-treated subjects who did not complete their RT course and did not have observed acute radiation esophagitis before discontinuing. Safety analyses will include all subjects who receive at least one dose of GC4419. Efficacy and safety may also be summarized for a “per protocol” population of subjects completing RT/chemotherapy and at least 5 weeks of GC4419.

### 12.4. Definition of Endpoints

#### 12.4.1. Primary Endpoint

Incidence of acute radiation esophagitis ( $\geq$  Grade 2; NCI-CTCAE version 5 through the end of chemoradiotherapy for NSCLC or SCLC when GC4419 is added).

#### 12.4.2. Secondary Efficacy Endpoints

- Incidence of acute severe (Grade 3-4) radiation esophagitis by the NCI-CTCAE scale (Grade 3-4) through the completion of chemoradiotherapy;

- Incidence of acute esophagitis  $\geq$  Grade 2 through 4 weeks after completion of chemoradiotherapy, using the NCI-CTCAE scale;
- Incidence of acute severe (Grade 3-4) radiation esophagitis through 4 weeks after completion of chemoradiotherapy;
- Presence of acute ( $\geq$  Grade 2) and acute severe (Grade 3-4) radiation esophagitis at evaluation 4 weeks after completion of chemoradiotherapy;
- Incidence of acute (through 90 days after radiation therapy) radiation pneumonitis,  $\geq$  Grade 2 by the NCI-CTCAE scale;
- Percentage weight change from baseline through the completion of chemoradiotherapy and 4 weeks after treatment.

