#### **10.7.4. Week 4**

Prior to RT administration, the following observations and procedures will be conducted for all subjects on **all RT days**:

- Record concomitant medications and need for parenteral or tube feeding
- Record AEs
- Conduct esophagitis assessment daily and record the severity using both the CTCAE and RTOG grading scales.
- Ensure the daily swallowing diary is completed.

Prior to GC4419 administration, the following observations and procedures will be conducted for all subjects **once this week**:

- Record analgesic / narcotic use
- Perform symptom-directed PE
- Have the patient complete the PROs and NPRS and review completion.
- Measure vital signs, body weight and ECOG Performance Status
- Draw blood for laboratory measurements:
  - Chemistry profile
  - Hematology profile
  - PK sampling (See [Section 10.3](#)) – Day 22 only

Administer GC4419 doses by continuous IV infusion. GC4419 should be administered so that RT is administered within 60 minutes of the end of the GC4419 infusion.

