#### **10.7.6. 4 Weeks Post-RT**

All subjects will be evaluated at  $28 \pm 15$  calendar days from the last day of RT. The following should be completed at this visit:

- Conduct a complete physical examination
- Measure vital signs, body weight, and ECOG status

- Record any concomitant medications including analgesic/narcotic use and need for parenteral or tube feeding
- Record AEs through 30 days after the last dose of RT
- Conduct Esophagitis assessment for the week and record the severity using both the CTCAE and RTOG scales
- Have the patient complete the PROs and NPRS review completion.
- Collect swallowing diary and ensure it was completed daily through 4 Weeks post-RT
- Draw blood for laboratory measurements:
  - Chemistry profile
  - Hematology profile

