#### **11.2.4. Disease-related Events and/or Disease-related Outcomes Not Qualifying as SAEs**

Esophagitis will not be reported as AEs as it is captured as a study endpoint in the CRF. Progressive disease found by scan or on clinical evaluation should be captured on the applicable CRF pages and not as an AE.

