#### **12.4.3. Exploratory Endpoints**

- Severity of radiation esophagitis-related pain, dysphagia, and dyspepsia during combined chemotherapy and RT using these fields of the NCI PRO-CTCAE weekly during treatment, and 4 weeks after completion of chemoradiotherapy;
- Incidence of acute esophagitis  $>$  Grade 2 through 4 weeks after completion of chemoradiotherapy, using the RTOG scale;
- Incidence of acute severe (Grade 3-4) radiation esophagitis through 4 weeks after completion of chemoradiotherapy, using the RTOG scale;
- Patient-reported dysphagia via a daily patient log and need for parenteral or tube feeding;
- Opioid use by collecting the patient's analgesic/narcotic use in the previous 24-hour period at each weekly evaluation.

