### **12.6.2. Handling of Missing Data**

Investigators should make reasonable attempts to continue to collect Esophagitis RTOG and CTCAE scores for inclusion in the study database for subjects who discontinue from study drug but continue to receive further RT fractions.

The trial’s statistical analysis plan will discuss the imputation strategy for subjects who lack Esophagitis scores, who discontinue from the trial without complete follow-up of Esophagitis scores, and whose resolution date of severe Esophagitis is unknown.

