## **12.7. Secondary Efficacy Analyses**

### **12.7.1. Incidence Endpoints**

Secondary incidence endpoints will be presented descriptively along with 95% Clopper-Pearson exact confidence intervals. Each incidence endpoint will have an analysis population that includes all subjects who receive at least one dose of GC4419 and either a) complete the follow-up period for the endpoint or b) discontinue follow-up early but are known to have had the endpoint.

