## APPENDIX 1. SCHEDULE OF ASSESSMENTS

Assessments	Screening Phase Within 28 days of RT start	Active Phase									Post Active Phase	
		Baseline RT Day 1	Wk 1 Days 2-7	Wk 2 Days 8-14	Wk 3 Days 15-21	Wk 4 Days 22-28	Wk 5 Days 29-35	Wk 6 Days 36-42	Last Day of RT or Early Term 	4 weeks from Last Day of RT (± 15 Days)	90 Days Post-RT (± 15 Days)	6, 9, 12 months post treatment (± 30 days)
Informed consent	X											
Inclusion/exclusion criteria	X	X										
Medical history 	X	X										
Complete Physical Exam	X								X	X	X	X
Height/Record BSA	X											
Symptom-directed Physical Exam						X						
Vital signs, ECOG and weight	X	X				X			X	X		
Serum pregnancy test	X											
Concomitant medications 		X	Weekdays						X	X		
Adverse Events 		X	Weekdays						X	X	X 	
Pneumonitis Assessment  : NCI-CTCAE scale, CT Scan, spirometry, and DLCO	X								X			X
Tumor assessment (Chest CT with or without contrast)	X										X	X
ECG (12-lead) 	X											
Esophagitis assessment—CTCAE 	X	X	Weekdays						X	X		
Esophagitis assessment—RTOG 	X	X	Weekdays						X	X		
Patient reported outcomes: NCI-PRO-CTCAE, NPRS 	X	X		X	X	X	X	X	X	X		
Patient-reported swallowing diary 	X	X	Daily including weekends						X	X		
Analgesic/narcotic use reporting		X	X	Weekly						X	X	
Parenteral/tube feeding use reporting			X	Weekly						X	X	
Blood draw: Lab safety tests 	X	X	X	X	X	X	X	X	X 	X		
Blood draw: PK 		X	X			X						
RT + chemotherapy parameters recorded	X	Per protocol schedule/standard regimen										
Dosing GC4419 		X	Days 2-5	Days 8-12	Days 15-19	Days 22-26	Days 29-33	Days 36-40				

BSA = Body Surface Area, CTCAE = Common Terminology Criteria for Adverse Events, DLCO = diffusing capacity of the lungs for carbon monoxide, ECG = Electrocardiogram, ECOG = Eastern Cooperative Oncology Group, NCI-PRO-CTCAE = National Cancer Institute-Patient Reported Outcome- Common Terminology Criteria for Adverse Events, NPRS = Numeric Pain Rating Scale, RT = Radiation Therapy, RTOG = Radiation Therapy Oncology Group.

- 1 If a subject ends study participation early and/or withdraws consent after first dose of GC4419, all last day of RT procedures should be completed.
- 2 Medical History should include NSCLC or SCLC cancer history including prior treatments and confirmation of histopathological diagnosis

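### One post-RT esophagitis grading, on Day 13 to 43, cannot fix incidence through 4 weeks in either direction; separately, the diary form conflicts with the protocol on post-RT entries

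*Combined protocol and SAP*

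**What the plan says.** Section 12.4.2 lists two cumulative incidences after treatment: acute esophagitis of at least "Grade 2 through 4 weeks after completion of chemoradiotherapy, using the NCI-CTCAE scale", and Grade 3-4 over the same period. It lists presence at the 4-week evaluation as a separate endpoint. Section 12.4.3 adds RTOG versions, including severe "radiation esophagitis through 4 weeks after completion of chemoradiotherapy, using the RTOG scale".

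During RT the instruction for every RT day is: "Conduct esophagitis assessment daily and record the severity using both the CTCAE and RTOG grading scales" (Section 10.7.4; Sections 10.7.2 and 10.7.3 match). Esophagitis is graded again at the last-day visit (10.7.5). After that, Section 10.7.6 schedules one grading: "Conduct Esophagitis assessment for the week and record the severity using both the CTCAE and RTOG scales". Appendix 1 times it at "4 weeks from Last Day of RT (± 15 Days"). The week is not defined. The 90-day visit lists no esophagitis grading.

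Section 11.2.4 closes the adverse-event route: "Esophagitis will not be reported as AEs as it is captured as a study endpoint in the CRF". Section 12.7.1 includes subjects who "complete the follow-up period for the endpoint" or who are known to have had the event. Section 12.6.2 leaves imputation to a separate SAP, including for subjects "whose resolution date of severe Esophagitis is unknown".

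On the diary, Sections 10.4.2 and 10.7.6 and Appendix 1 footnote 9 require daily entries until the 4-week post-RT visit. The Appendix 6 entry schedule is daily during RT, then at end of treatment and 12 weeks after radiation. It sets the final hand-in at 12 weeks from the start of treatment.

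**The concern.** The protocol separates ever having had esophagitis by 4 weeks from having it at the 4-week visit, but the post-RT schedule collects data suited mainly to the second. A cumulative incidence needs each first occurrence up to the cut-off and a way to tell whether it fell before or after. One grading of one week, with no scheduled onset date and a 30-day span of possible visit days, supplies neither.

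At stake are the two secondary incidences, their RTOG counterparts and the presence endpoint, whose value depends partly on when the visit falls. A patient who follows the diary form's entry schedule would also leave out four weeks of post-RT entries that the exploratory dysphagia endpoint relies on.

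**Working it through.** **Window.** 28 - 15 = 13 and 28 + 15 = 43, so the visit falls on post-RT Day 13 to 43.

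**Coverage.** Assume the graded week is the 7 days ending on visit day v, that is, Days v-6 to v.

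| Visit day | Graded days | Days 1-28 covered | Not covered |
|---|---|---|---|
| 13 | 7-13 | 7 | 1-6 and 14-28 (21 days) |
| 28 | 22-28 | 7 | 1-21 (21 days) |
| 35 | 29-35 | 0 | all 28 |
| 43 | 37-43 | 0 | all 28 |

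This gives three ways to misclassify a subject who did not reach the threshold during RT:
- Onset after RT and resolution before Day v-6: no scheduled grade, incidence too low.
- Onset after a visit held before Day 28: no scheduled grade, incidence too low.
- Onset after Day 28 but graded at a Day 29-43 visit: counted unless dated, incidence too high.

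**How far the size depends on assumptions.** The documents give no rate or timing of post-RT first onset. The only usable duration is 1.6 months of symptomatic esophagitis with conventional RT plus carboplatin (Section 4.1.2.2), which is not labelled as mean or median. 1.6 × 30.44 = 48.7 days as a mean. Read as an exponential median, the mean is 48.7 / ln 2 = 70.3 days. Assume first onset is uniform, at a rate of 1/28 of the Day 1-28 onsets per day. With S(t) the chance that an episode lasts beyond t days:
- Missed share = average over onset days d = 1 to 28 of: 1 if d > v; 1 - S(v-6-d) if d < v-6; 0 otherwise.
- Added share (v > 28, same onset rate continuing to the visit) = (1/28) × sum over d = 29 to v of: S(v-6-d) if d < v-6; 1 otherwise.
- S(t) = exp(-t/48.7) or exp(-t/70.3) for the exponential; exp(-x)(1 + x + x²/2 + x³/6) with x = 4t/48.7 for a gamma of shape 4; 1 up to 48.7 days and 0 after for a fixed duration.

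| Duration shape | Missed, v=13 | Missed, v=28 | Missed, v=43 | Added, v=43 |
|---|---|---|---|---|
| Exponential, mean 48.7 | 55.0% | 14.7% | 36.1% | 51.1% |
| Exponential, median 48.7 | 54.6% | 10.6% | 26.9% | 51.8% |
| Gamma shape 4, mean 48.7 | 53.6% | 2.0% | 13.8% | 53.5% |
| Fixed 48.7 | 53.6% | 0.0% | 0.0% | 53.6% |

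All shares are relative to first onsets on post-RT Days 1-28. At a Day 28 visit, with the 48.7-day mean, the missed share is 0% to 15% and comes entirely from the shape. At Day 43 the added cases exceed the missed ones in every row, so under these assumptions the net error there is upward. At Day 13 almost all of the loss is onset after the visit (15/28 = 53.6%). The figures concern Grade 2 or worse; no Grade 3-4 duration is given.

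**One case.** Section 12.2 illustrates with 9/55 = 16.4%. One case is 1/55 = 1.8 points: 8/55 = 14.5%, 10/55 = 18.2%.

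**Presence at 4 weeks.** For cases present at the end of RT, exponential durations leave exp(-t/48.7) = 77%, 56% and 41% on Days 13, 28 and 43 (83%, 67% and 54% with 70.3). This only illustrates the dependence on visit day.

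**Diary.** Under the Appendix 1 calendar the last RT day is Day 40 for 30 fractions, or Day 47 for 35. The form's last entry, 84 days later, falls on Day 124 or 131. Its last hand-in is about Day 84, which is 40 to 47 days earlier. The form therefore conflicts with the protocol on post-RT entries and uses two time references of its own.

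**The case against.** Several counter-arguments carry weight.

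- **Other data exist.** Narcotic and concomitant-medication records, tube or parenteral feeding and the diary leave traces. They carry no CTCAE or RTOG grade, and feeding bears on Grade 3 rather than Grade 2.
- **The CRF may already hold dates.** Section 11.2.4 says the CRF captures esophagitis as an endpoint, and Section 12.6.2 expects resolution dates for severe episodes. Some severe episodes may therefore be dated already. The CRF and the separate SAP are not in the file, so this point covers only what the protocol schedules.
- **The Day 28 cut-off is one reading.** The Section 5.2 objectives are worded more loosely, and maximum grade through the 4-week visit would fit the schedule. Follow-up would then range from 13 to 43 days between subjects. Completion of chemoradiotherapy may also be later than the last RT day, since Sections 8.1 and 11.2.2 allow chemotherapy to finish last.
- **The window is deliberate.** The revision history gives pandemic flexibility as the reason, and the window can stay.
- **The diary harm is limited.** The form opens by asking for a record each day of the week, and sites must check daily completion (10.7.6). Exclusion criterion 5 mentions an electronic device, so it is unclear whether patients use the paper form. The written instructions still conflict.

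A reader might infer that the incidences are simply biased low. The documents do not support that, because visits after Day 28 can add cases. A reader might also infer that the form supplies too few sheets. It promises a minimum number plus extras, so there is no contradiction.

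**Conclusion.** The point holds as a minor one. As scheduled, the through-4-weeks incidences can err in either direction, and presence at 4 weeks mixes status from Day 13 to Day 43. Neither the number of misclassified cases nor the net direction can be derived. The 0% to 15% missed at a Day 28 visit rests on a 7-day graded week, uniform onset and a 48.7-day mean duration. The firm figure is 1.8 points per misclassified case at n=55.

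A reader might extend the doubt to the primary result. That is not supported: the primary endpoint ends with chemoradiotherapy and is graded on every RT day, and cases first graded during RT are already in the later incidences. The endpoints concerned are secondary or exploratory and descriptive (Section 12.6.1). The diary conflict is a separate matter of wording and needs no model.

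**What to change.** 1. At the existing 4-week visit keep the current grading. Unless the CRF already does so, also record on each scale whether Grade 2 or worse, and whether Grade 3-4, has occurred since the last RT day, with a first-onset date for each. Count onsets on or before Day 28, state whether the clock starts at last RT or last chemotherapy, and report how many events rest on recall only.
2. Keep subjects seen before Day 28 in the analysis and report their number. Add a sensitivity analysis, for example a Kaplan-Meier estimate at Day 28 with event-free subjects censored at their visit. Section 12.7.1 should not be applied so that event-free early-visit subjects drop out while events stay. As pure arithmetic, with 9/55 events and half of the 46 event-free subjects seen early, 16% would become 9/(9 + 23) = 28%.
3. Report the distribution of actual visit days beside presence at 4 weeks.
4. Reconcile Appendix 6 with Sections 10.4.2 and 10.7.6 and Appendix 1 footnote 9, using one time reference.

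The cost is at most eight CRF fields (two scales, two thresholds, yes/no and date), one sensitivity analysis, one table and a corrected form, with no added visit. The downside is that recalled grades and dates are less reliable than same-day grading. Recall also cannot cover the days after an early visit, which is why item 2 is needed.
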